#### 7.3.4 Replacement of Subjects

A subject who withdraws from the study will not be replaced.

### 7.4 Treatments

The investigator will take responsibility for and will take all steps to maintain appropriate records and ensure appropriate supply, handling, storage, distribution, and use of study materials in accordance with the protocol and any applicable laws and regulations.

#### 7.4.1 Dosage and Formulations

The following study devices will be used in the study and provided by the Sponsor:

**Test device:** PN40082 (manufactured by Prollemium Medical Technologies) is a clear, colorless gel in 1.0 mL pre-filled syringes with 25 mg/mL of stabilized hyaluronic acid and lidocaine 0.3% w/w.

**Comparator device:** Restylane Silk (manufactured by Q-Med AB for Medicis – A Division of Valeant Pharmaceuticals Corporation North America, LLC ) is a clear, colorless gel in 1.0 mL pre-filled syringes formulated to a concentration of 20 mg/mL of stabilized hyaluronic acid and lidocaine 0.3% w/w.

#### 7.4.2 Randomization

Subjects who satisfy all of the eligibility criteria will be randomized in a 1:1 ratio to treatment with PN40082 or Restylane Silk. Randomization will be performed according to a computer-generated randomization scheme that will be generated and maintained by an independent third party. A sealed copy of the randomization scheme should be retained at each site and should be available to regulatory authorities at the time of site inspection to allow for verification of the treatment identity for each subject.

A unique subject number will be assigned to each subject. Each site will receive the randomization scheme. Each eligible subject will be assigned a unique randomization code number in ascending order.

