### **7.3.1 Inclusion Criteria**

Subjects must meet all of the following criteria to be eligible for the study:

1. Men or non-pregnant or non-breastfeeding women over 21 years of age
2. If female and of childbearing potential, a negative urine pregnancy test at Baseline (Day 1) and the subject agrees to use adequate contraception during the study period

3. Has an overall score of very thin or thin on the LFGS, as agreed upon by the Treating and Evaluating Investigators, and desires at least a 1-point improvement in overall LFGS score; OR  
Has a Fitzpatrick skin phototype IV, V or VI and has an LFGS score of thick or full, as agreed upon by the Treating and Evaluating Investigators, and desires treatment to the vermilion body of 1 or both lips
4. Willing to give written informed consent

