#### **7.4.4 Blinding of Study Device**

Injections of the study device are performed by the unblinded Treating Investigator. The blinded Evaluating Investigator is not allowed to retrieve study supplies or to be present during opening of the study supplies or during the injections. The Treating Investigator is not to have any discussion with the Evaluating Investigator or subjects regarding the treatments.

Subjects are blinded to treatment assignment. Subjects are physically masked (blindfolded) just prior to and during all injection procedures to prevent observation of the syringes containing study device.

Subjects, investigators, the Sponsor's staff conducting the study, and members of the administrative team will not have access to individual subjects' treatment assignments. In the event of an emergency that requires breaking of the study blind, the randomization code will be maintained by each investigator that can be opened to reveal the study device.

See Section 7.9.10.2 for a description of the method of unblinding a subject during the study if such action is warranted.

At Visit 5, subjects and blinded evaluating investigators will be asked which treatment they thought was administered as a way of evaluating the blinding.

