##### **7.9.10.2 Unblinding Treatment for a Subject During the Study**

Unblinding by the investigator should occur only in the event of an AE or SAE for which it is necessary to know the study treatment to determine an appropriate course of therapy for the subject. In the event of an emergency that requires breaking of the study blind, the Investigator can unblind the subject without prior contact with the Medical Monitor although the Investigator will immediately notify the Medical Monitor accompanied by a written explanation of the reason why the blind was broken. In the event of an emergency that requires breaking of the study blind, the randomization code will be maintained by each unblinded Treating Investigator that can be opened to reveal the study device to the applicable staff. In the event the unblinded Treating Investigator is not available, the site should designate another unblinded staff member not involved in the study conduct to access the randomization code for that

subject. Note this can be done WITHOUT informing the blinded Evaluating Investigator and thus maintaining the study blind. If unblinding occurs, the subject must be withdrawn from the study.

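### Allocation concealment up to enrollment is not ensured: sites receive the randomization scheme, custody statements conflict, and no per-subject release step is described

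*Protocol*

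**What the plan says.** **Who keeps the scheme.** Protocol 7.4.2 says it is "generated and maintained by an independent third party". The same paragraph adds "A sealed copy of the randomization scheme should be retained at each site", for the purpose of verification at inspection. The next paragraph says "Each site will receive the randomization scheme" and "Each eligible subject will be assigned a unique randomization code number in ascending order".

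**Who keeps the code.** Protocol 7.9.10.2, on emergency unblinding, says "the randomization code will be maintained by each unblinded Treating Investigator that can be opened to reveal the study device". Protocol 7.4.4, on the same emergency, says "the randomization code will be maintained by each investigator that can be opened to reveal the study device". One sentence earlier, 7.4.4 says that subjects, investigators and sponsor staff "will not have access to individual subjects' treatment assignments".

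**Who decides entry.** Inclusion criterion 3 in Protocol 7.3.1 requires a lip-fullness (LFGS) category "as agreed upon by the Treating and Evaluating Investigators". Protocol 7.6.9 has the Treating Investigator score LFGS at Visit 1. Exclusion 8 in 7.3.2 is left to that investigator's judgement. SAP 3.1 has the same person carry out the baseline assessments that confirm the entry criteria. Protocol 7.7.1 places eligibility, randomization and injection at one visit, in that order.

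**How the product is identified.** In Protocol 7.4.5 the label described for the PN40082 carton identifies the protocol and the sponsor, and Restylane Silk comes in its commercial packaging. No randomization number is mentioned for either.

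**The concern.** Randomization protects the comparison only if the person deciding on entry cannot foresee the next arm. Here the Treating Investigator is unblinded, keeps the code, works at a site that receives the scheme, and shares the entry decision. If the next assignment could be known, a borderline subject could be accepted, deferred or refused in light of it.

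Who enters matters for this endpoint. LFGS runs from 0 to 4. Eligible subjects range from very thin lips to, for Fitzpatrick types IV to VI, full lips. A subject entering at 0 can gain up to four grades and one entering at 4 can gain none. Selective entry could therefore shift the difference in mean or median change in either direction. The primary analysis in SAP 5.5.1 uses Hodges-Lehmann limits with no adjustment for baseline LFGS or site, so it would not offset a resulting imbalance.

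**Working it through.** The plan gives no figure on concealment to reproduce. The check compares the passages and then illustrates what could be foreseen under stated assumptions.

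1. **Is the list at the site sealed?** The first paragraph of 7.4.2 says sealed and gives inspection as the purpose. The second says that the site receives the scheme and ties it to assigning numbers in sequence, with no mention of a seal. The two can be read as one sealed document or as two documents, and the text does not settle which.

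2. **How does a code number become a product?** A list sealed for inspection cannot also be the working tool for assignment unless something else does that job. Neither document describes central or web release, per-subject envelopes, or kits numbered to the scheme. Protocol 7.4.3 mentions a device kit for the subject and 7.4.6 says device is on site for each subject, but neither links a kit to a randomization number. Protocol 7.6.1 makes the Treating Investigator responsible for giving the correct randomized device.

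3. **Who can open the code?** Section 7.9.10.2 says the unblinded Treating Investigator. Section 7.4.4 says each investigator, which taken literally includes the blinded evaluator. The access denial in 7.4.4 cannot be literally true of an unblinded Treating Investigator. The three statements do not fit together.

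4. **Does that person help decide entry?** Yes, under Protocol 7.3.1, 7.3.2 (exclusion 8) and 7.6.9 and SAP 3.1.

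5. **How much could be foreseen?** Inputs: 158 subjects, approximately 7 sites, 1:1 allocation. That is 158/7 = 22.6, or about 23 subjects per site.
   - *List open at the site:* 100% of upcoming assignments are known.
   - *List sealed:* the unblinded Treating Investigator still knows the earlier assignments that he or she injected. Assume fixed permuted blocks of size 2m within site, block size known, and all earlier assignments at the site known. The documents give no block size, so a range is shown. The assignments known with certainty are those in the final run of each block. That run has expected length 2m/(m+1), so the share is 1/(m+1). Best-guess accuracy is 1/2 + (4^m / C(2m,m) − 1)/(4m).

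| Block size | Known with certainty | Of 158 | Best-guess accuracy |
|---|---|---|---|
| 2 (m=1) | 1/2 = 50% | 79 | 0.5 + (2 − 1)/4 = 75% |
| 4 (m=2) | 1/3 = 33% | about 53 | 0.5 + (2.667 − 1)/8 = 71% |
| 6 (m=3) | 1/4 = 25% | about 40 | 0.5 + (3.2 − 1)/12 = 68% |
| 8 (m=4) | 1/5 = 20% | about 32 | 0.5 + (3.657 − 1)/16 = 67% |

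These are shares of assignments that could be foreseen. They are not estimates of bias, which would also need to know how often foresight changed an entry decision and by how much response differed. The documents give neither.

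**The case against.** A reader might infer that allocation is simply open at the sites. The text does not support that. A third party maintains the scheme and the site copy is called sealed. The sentence about sites receiving the scheme may describe that same copy, since a site cannot keep what it was never sent.

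A reader might also infer that whoever injects must read the list. No passage says so. Kits are mentioned, and 7.6.1 allows separate unblinded staff to help manage the device, so an injector could be handed one subject's product. The custody wording in 7.4.4 and 7.9.10.2 concerns emergencies and a code that is closed until opened. Section 7.9.10.2 also speaks of the code for the subject concerned, which suggests individual codes. Holding a closed emergency code is not foreknowledge of the next arm.

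Nor do the documents establish that the blinded evaluator holds the code. Section 7.4.4 refers on to 7.9.10.2, which narrows custody to the Treating Investigator and notes that unblinding need not involve the evaluator.

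There are real safeguards as well. The blinded evaluator must agree the entry score, only subjects who already meet the criteria are randomized, and the procedure list puts eligibility first.

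All of this stands against a claim that concealment has failed. It does not supply the missing release step. The evaluator's agreement guards the LFGS score but not exclusion 8 or a decision to defer a subject. Order in a list of procedures does not stop the next assignment from being known beforehand.

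**Conclusion.** The point holds in this form: concealment up to enrollment is not ensured by the plan. The next assignment is potentially knowable to someone who shares the entry decision, and the passages on custody and access contradict each other. The contradiction is certain from the text. An actual breach is not shown, and the bias cannot be sized.

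The illustration runs from 20% to 50% of assignments deducible under a sealed list with fixed known blocks of 8 down to 2, and to 100% under an open list. It rests on the block assumptions stated with it. This is more than missing detail, because the custody the plan does describe is weaker than a standard alternative that costs little, and the primary analysis is unadjusted. It is a cheap improvement that should be made.

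**What to change.** - In Protocol 7.4.2, replace site receipt of the scheme with sequentially numbered, opaque, individually sealed envelopes, or kits numbered to the scheme, prepared by the third party.
- State that each is opened only after both investigators have signed eligibility and the baseline LFGS. The opener should preferably be unblinded staff of the kind 7.6.1 already allows, with no role in eligibility.
- Keep any block details out of documents that sites hold. Envelopes do not by themselves stop deduction from past assignments, and withholding block details limits it without removing it.
- Keep emergency codes separate from the allocation list.
- Reconcile 7.4.4 with 7.9.10.2 so that the blinded Evaluating Investigator holds no code, and restrict the access denial in 7.4.4 to the people it can truly cover.

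The cost is protocol wording plus preparing and accounting for envelopes or kit labels. No central system is needed and the sample size of 158 does not change. Section 7.6.1 makes separate unblinded staff optional, so a site without them must either name someone or let the Treating Investigator open the envelope after both signatures. If enrollment has begun, record who held the scheme at each site and when assignments were opened.

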#### 7.4.3 Study Device Administration

Subjects are physically masked (blindfolded) just prior to and during all injection procedures to prevent observation of the syringes containing study device. Any unblinded investigators and staff should be reminded NOT to discuss the treatment in the presence of the subject.

The subject should be positioned in a seated position and may be reclined to as much as 45°.

Any makeup should be removed with a gentle cleanser or a specific makeup remover product (such as Neutrogena Cleansing Makeup Remover Facial Wipes).

The non-vermillion areas of the upper and lower lips should be prepared by gentle washing with a surgical scrub product (Chlorhexidine, Technicare, etc.).

To prepare the syringes for use, the investigator should attach one of the needles included in the subject study device kit in a firm manner. The plunger should be gently depressed to express any unwanted air

until a small droplet of implant material appears at the tip of the needle.

Study device is administered using only a needle provided in the subject study device kit. The needle is inserted at an approximate angle of 30° parallel to the surface of the skin or lip. For rhytids, study device should be injected into the mid-to-deep dermis. Study device should be injected into the submucosal layer for lip augmentation; care should be taken to avoid intramuscular injection. If study device is injected too superficially this may result in visible lumps and/or bluish discoloration.

Inject study device applying light to moderate, even pressure on the plunger. Avoid injecting quickly as rapid injection can result in increased pain. It is important that the injection is stopped just before the needle is pulled out of the skin to prevent material from leaking out or being too superficially implanted into the skin.

Only correct or augment to 100% of the desired volume effect. Do not overcorrect or overfill.

The needle may be replaced as needed to ensure subject comfort. Only needles provided in the subject study device kit may be used. Before needle replacement, the plunger should be withdrawn slightly and once the needle has been replaced, the plunger re-advanced to ensure that the new needle is prefilled with implant material prior to restarting injections.

Typical usage for each treatment session is specific to the site as well as the amount of augmentation or rhytids correction desired. Based on U.S. clinical studies, the maximum volume allowed per treatment is 1.5 mL per lip (1.5 for upper, 1.5 for lower) and 1.0 mL for perioral rhytid correction. Thus, the maximum amount that can be used at one treatment session is 4.0 ml.

Amounts of material injected should be recorded separately for the upper lip, lower lip and perioral areas.

## INJECTION TECHNIQUES

1. Study device can be injected by a number of different techniques that depend on the treating investigator's experience and preference and subject characteristics.
2. **Serial puncture** involves multiple, closely spaced injections along wrinkles, folds, or the vermilion border. Although serial puncture allows precise placement of the filler, it produces multiple puncture wounds that may be undesirable to some subjects.
3. **Linear threading (includes retrograde and antegrade)** is accomplished by fully inserting the needle into the center of the area to be corrected or augmented and injecting the filler along the track as a "thread." Although threading is most commonly practiced after the needle has been fully inserted and is being withdrawn, it can also be performed while advancing the needle - antegrade technique). To augment the lip, the retrograde linear threading technique is the most advisable.
4. Serial threading is a technique that utilizes elements of both approaches.

Note! The correct injection technique is crucial for the final result of the treatment.

5. The following techniques should be avoided as they may result in an increase in short-term episodes of bruising, swelling, redness, pain, or tenderness at the injection site:
  - Dissection of the sub-epidermal plane with lateral movement of the needle – "fanning"
  - Rapid flow rate (> 0.3 mL/min) of implant material injection
  - High injection volumes
  - The use of needles other than ones provided in the subject study device kit
6. The use of cannulas is prohibited.

7. When the injection is completed, the treated site should be **gently** massaged so that it conforms to the contour of the surrounding tissues. Massaging that substantially deforms the lips or causes blanching of compressed tissues is excessive and should be avoided except as described below.
8. If excessive material is implanted or irregularly implanted, massage the area somewhat more firmly than for the usual implantation procedure to obtain optimal results.
9. If blanching of the tissues is observed during or directly after injection and becomes a concern, the area may be gently massaged. If blanching persists, contact the Medical Monitor.
10. The lips should be augmented to achieve the maximum desirable appearance for both the treating investigator and the subject. Subjects should be provided a small hand mirror to observe the results and further injections conducted until maximum benefit has been obtained. Care should be taken to ensure that the lips are symmetric from right to left and that the upper and lower lips have relative proportionality.
11. The perioral area should be corrected AFTER the upper and lower lips have been corrected. Some correction of perioral rhytids may occur with lip augmentation, thus it is best to address any remaining perioral correction needs after the lip injections have been completed.
12. If the treated area is swollen directly after the injection, an ice pack can be applied on the site for a short period if the investigator deems it appropriate. Ice should be used with caution if the area is still numb from anesthetic to avoid thermal injury.
13. Subjects should be encouraged to avoid a recumbent position for several hours after injections to reduce swelling. The use of ice, cold packs or other therapies to reduce swelling should only be performed at instruction of the investigator. The subject should be instructed to contact the site if substantial swelling occurs.

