#### **10.5 Modifications to the Protocol**

The procedures defined in the protocol and CRFs will be carefully reviewed to ensure that all parties involved with the study fully understand the protocol. To ensure the validity of the data, no deviations from the protocol (with minimal exceptions) may be made unless the issue is broad enough to warrant revision of the protocol. Such revisions must be submitted to and have documented approval from the Sponsor and IRB prior to implementation. The only circumstance in which an amendment may be initiated without prior IRB approval is to eliminate an apparent immediate hazard to a subject or subjects. In such a case, however, the investigator must notify the Sponsor immediately and the IRB within 5 working days after implementation.

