#### **Preparation:**

- The above materials should be gathered and labeled for emergency use only (to ensure they are available should an urgent situation arise).
- Staff should be educated regarding the urgent nature of such an event and the location of all materials and contact information.
- Investigators may wish to familiarize themselves with the retrobulbar injection technique via literature or on line training.

It is critical to recognize any intravascular events during injections and act quickly to maximize likelihood of reversal. As soon as an intravascular is recognized, **stop any further injections.**

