#### **If a skin infarction is identified:**

- Apply nitroglycerin paste – apply liberally to the affected area and massage in gently, expect headache complaint from subject but do not withhold the treatment.
- Massage area to help promoted blood flow
- Dispense Aspirin 325 mg - Have patient chew this or the aspirin may be placed sublingually for maximum rapid absorption
- If blanching persists, consider infiltration with hyaluronidase
  - Infiltrate in the area where material was being injected – this may allow hyaluronidase to enter the same vessel that was inadvertently cannulated.
  - Infiltrate in the area of blanching or ischemia as well
  - Inject a minimum of 50 units into each area; investigators are free to use larger doses as they see fit.
  - Hyaluronidase may be repeated as needed.
- Hot Packs – Towels or gel packs warmed in a microwave can be applied to the area of decreased blood flow.
- Monitor the subject and the area of blanching ischemia. If blanching persists after 24 hours,– consider hyperbaric oxygen treatments.

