## INJECTION TECHNIQUES

1. Study device can be injected by a number of different techniques that depend on the treating investigator's experience and preference, and patient characteristics.
2. **Serial puncture** involves multiple, closely spaced injections along wrinkles, folds or the vermilion border. Although serial puncture allows precise placement of the filler, it produces multiple puncture wounds that may be undesirable to some patients.
3. **Linear threading (includes retrograde and antegrade)** is accomplished by fully inserting the needle into the center of the area to be corrected or augmented and injecting the filler along the track as a "thread." Although threading is most commonly practiced after the needle has been fully inserted and is being withdrawn, it can also be performed while advancing the needle - antegrade technique). To enhance the lip, the retrograde linear threading technique is the most advisable.
4. Serial threading is a technique that utilizes elements of both approaches.

Note! The correct injection technique is crucial for the final result of the treatment.

5. The following techniques should be avoided as they may result in an increase in short-term episodes of bruising, swelling, redness, pain, or tenderness at the injection site:
  - Dissection of the sub-epidermal plane with lateral movement of the needle – "fanning"
  - Rapid flow rate (>0.3 mL/min) of implant material injection
  - High injection volumes
  - The use of needles other than those provided in the treatment kit
6. The use of cannulas is prohibited
7. When the injection is completed, the treated site should be **gently** massaged so that it conforms to the contour of the surrounding tissues. Massaging that substantially deforms the lips, or causes blanching of compressed tissues, is excessive, and should be avoided except as described below.
8. If excessive material is implanted or irregularly implanted, massage the area somewhat more firmly than for the usual implantation procedure to obtain optimal results.
9. If blanching of the tissues is observed during or directly after injection, pause the procedure and massage the area gently until the color returns. If the condition persists, contact the Medical Monitor.

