**WARNINGS**

- Defer use of *Restylane Silk* at specific sites in which an active inflammatory process (skin eruptions such as cysts, pimples, rashes, or hives) or infection is present until the process has been controlled.
- Injection site reactions (e.g., lip swelling, lip pain, and contusion) to *Restylane Silk* have been observed as consisting mainly of short-term minor or moderate inflammatory symptoms starting shortly after treatment, with an average of less than 18 days duration in the lips. In some cases delayed onset of these events has been observed with a range of 21 to 142 days after treatment. Most events with delayed onset resolved within 18 days. Injection site swelling appears to occur more frequently with the linear antegrade method of injection. Rare post-market *Restylane* reports of immediate post-injection reactions included extreme swelling of lips, the whole face and symptoms of hypersensitivity such as anaphylactic shock.
- Introduction of product into the vasculature may lead to embolization, occlusion of the vessels, ischemia, or infarction. Take extra care when injecting soft tissue fillers, for example inject the product slowly and apply the least amount of pressure necessary. Rare but serious adverse events associated with the *intravascular* injection of soft tissue fillers in the face have been reported and include temporary or permanent vision impairment, blindness, cerebral ischemia or cerebral hemorrhage, leading to stroke, skin necrosis, and damage to underlying facial structures. Immediately stop the injection if a patient exhibits any of the following symptoms, including changes in vision, signs of a stroke, blanching of the skin, or unusual pain during or shortly after the procedure. Patients should receive prompt medical attention and possibly

evaluation by an appropriate health care practitioner specialist should an intravascular injection occur.

- *Restylane Silk* must not be implanted into blood vessels. Localized superficial necrosis and scarring may occur after injection in or near vessels, such as in the lips, nose, or glabellar area. It is thought to result from the injury, obstruction, or compromise of blood vessels.
- Delayed onset inflammatory papules have been reported following the use of dermal fillers. Inflammatory papules that may occur rarely should be considered and treated as a soft tissue infection.

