Vascular compromise may occur due to an inadvertent intravascular injection or as a result of vascular compression associated with implantation of any injectable product. This may manifest as blanching, discoloration, necrosis or ulceration at the implant site or in the area supplied by the blood vessels affected; or rarely as ischemic events in other organs due to embolisation. Isolated rare cases of ischemic events affecting the eye leading to visual loss, and the brain resulting in cerebral infarction, following facial aesthetic treatments have been reported.

Vision abnormalities including blindness have been reported following injection of hyaluronic acid fillers into the nose, glabella, periorbital areas, and/or cheek, with a time to onset ranging from immediate to a few days following injection. Reported treatments include anticoagulant, epinephrine, aspirin, hyaluronidase, steroid treatment and hyperbaric oxygen. Outcomes ranged from resolved to ongoing at the time of last contact. Events requiring medical intervention, and events where resolution information is not available were reported. In these cases, the product was injected into the highly vascularized areas of the glabella, nose, and periorbital area, which are outside the device indications for use (See Warnings section).

Adverse reactions should be reported to Galderma Laboratories, L.P. at [name].

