**Note! The correct injection technique is crucial for the final result of the treatment.**

**A. Serial Puncture (only recommended for needle)**

**B. Linear Threading (includes retrograde and antegrade)**

5. Dissection of the sub-epidermal plane with lateral movement of the needle, rapid flows ( $\geq 0.3$  mL/min), rapid injection or high volumes may result in an increase in short-term episodes of bruising, swelling, redness, pain, or tenderness at the injection site.
6. When the injection is completed, the treated site should be gently massaged so that it conforms to the contour of the surrounding tissues. If an overcorrection has occurred, massage the area firmly between your fingers or against an underlying area to obtain optimal results.
7. If so called “blanching” is observed, i.e., the overlying skin turns a whitish color, the injection should be stopped immediately and the area massaged until it returns to a normal color. Blanching may represent a vessel occlusion. If normal skin coloring does not return, do not continue with the injection. Treat in accordance with the American Society for Dermatologic Surgery guidelines, which include hyaluronidase injection.
8. If the wrinkles or lips need further treatment, the same procedure should be repeated until a satisfactory result is obtained. Additional treatment with *Restylane Silk* may be necessary to achieve the desired correction.
9. If the treated area is swollen directly after the injection, an ice pack can be applied on the site for a short period. Ice should be used with caution if the area is still numb from anesthetic to avoid thermal injury.
10. Patients may have mild to moderate injection site reactions, which typically resolve in less than 18 days in the lip.

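### Protocol 7.4.3 item 9 responds to blanching more weakly than both device Instructions for Use in the same document, and does not tell the injector to pause or stop

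*Protocol*

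**What the plan says.** Protocol 7.4.3, Injection Techniques, item 9: "If blanching of the tissues is observed during or directly after injection and becomes a concern, the area may be gently massaged". Its only other sentence sends the injector to the Medical Monitor if blanching persists.

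The PN40082 IFU, Injection Techniques item 9, covers the same situation without the qualifier. On any observed blanching the injector is to "pause the procedure and massage the area gently until the color returns", and to contact the Medical Monitor if the condition persists.

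The Restylane Silk IFU is stricter still. Its Warnings say: "Immediately stop the injection if a patient exhibits any of the following symptoms, including changes in vision, signs of a stroke, blanching of the skin". Item 7 of its Injection Techniques repeats the immediate stop, directs massage back to normal color, and adds: "Blanching may represent a vessel occlusion. If normal skin coloring does not return, do not continue with the injection". It then refers to specialist-society guidelines that include hyaluronidase injection. Its Post-Marketing Surveillance section describes vascular compromise as "associated with implantation of any injectable product. This may manifest as blanching, discoloration, necrosis or ulceration at the implant site", so the warning sign is not presented as peculiar to Restylane Silk.

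Protocol Appendix 1, the filler first aid protocol, orders injections to cease, but the trigger is "As soon as an intravascular is recognized" (the word for the event is missing in the source). Its treatment step "If blanching persists, consider infiltration with hyaluronidase" stands under the heading for an identified skin infarction.

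**The concern.** Blanching during a filler injection can be the first visible sign of a blocked vessel, and the comparator's IFU says so. Appendix 1 itself stresses early recognition and quick action. Item 9 governs the moment before recognition. There it leaves action to whether the injector is worried, makes massage optional and omits a halt. An injector who relies on item 9 alone is not told to do what either device text requires at that moment.

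What is at stake is subject safety in both arms. In the control arm, item 9 falls below the marketed comparator's own label. In the test arm, the pause in IFU item 9 is the only halt for blanching in the PN40082 IFU, whose Warnings have no counterpart to the Restylane Silk stop instruction. Item 9 of the protocol leaves that pause out.

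**Working it through.** No power, margin or error-rate calculation applies. The check sets the texts side by side and then looks for anything elsewhere in the protocol that supplies the missing instruction.

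**Step 1: the three blanching instructions.**

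| Element | Protocol 7.4.3 item 9 | PN40082 IFU item 9 | Restylane Silk IFU (Warnings; Injection Techniques item 7) |
|---|---|---|---|
| Trigger | Blanching seen and judged worrying | Any blanching seen | Any blanching seen |
| Halt | None | Pause | Immediate stop |
| Massage | Optional, no endpoint | Directed, until color is back | Directed, until color is normal |
| Blanching persists | Contact Medical Monitor | Contact Medical Monitor | Do not continue; treat per guidelines including hyaluronidase |

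Against the PN40082 IFU, item 9 lacks three elements: the unconditional trigger, the pause, and directed massage with an endpoint. The step for persistent blanching is the same. Against the Restylane Silk IFU it is weaker in all four rows.

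**Step 2: is this general paraphrase or an isolated weakening?** The protocol and the PN40082 IFU each list 13 parallel Injection Techniques items. Ignoring punctuation:

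- 7 are identical in wording (items 4, 6, 7, 8, 10, 11, 13);
- 4 differ only in synonyms such as subject/patient or the name of the kit (items 1, 2, 3, 5);
- 1 adds investigator discretion over ice packs (item 12);
- 1 loses a safety action (item 9).

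7 + 4 + 1 + 1 = 13. Item 9 is the only item that loses one.

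**Step 3: does another part of the protocol supply the halt?**

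- Appendix 1 does, but only after an intravascular event has been recognized. Item 9 does not refer to it. The pointer to Appendix 1 is in Section 7.9.3.4, on adverse events of special interest.
- No passage gives the IFUs precedence over 7.4.3. Where the protocol body relies on the device texts, it does so for storage (7.4.5) and for expectedness of adverse events (7.9.6.3).
- Section 7.6.1 makes the Treating Investigator responsible for administration according to the protocol and other study instructions, and Section 10.5 bars deviations with minimal exceptions. Section 7.4.3 is therefore an operative instruction.
- Item 10, immediately after item 9, directs further injection until maximum benefit is reached, with no exception for blanching.

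The halt is therefore missing from item 9, and Appendix 1 restores it only for events already recognized.

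**The case against.** The strongest reply is that item 9 is never read alone. Both IFUs are bound into the protocol and could count as other study instructions. The injector is unblinded, so knows which device is in use and which IFU applies. An experienced injector may stop anyway. Taken together, the protocol can be read as tiered: minor blanching under item 9, persistent blanching to the Medical Monitor, and a recognized vascular event under Appendix 1. Item 7 also mentions blanching caused by over-firm massage, which gives some basis for leaving room for judgment.

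Much of this stands, and it limits the point. It does not explain why the pause was left out, and no text says that the IFU prevails.

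Three stronger readings are tempting, and the documents support none of them:

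- *That the protocol tells the injector to keep going, or makes compliance impossible.* Item 9 is silent on stopping; it does not order continuation. Stopping satisfies all three texts.
- *That the protocol has no stop instruction at all.* Appendix 1 has one.
- *That item 9 would distort the root-cause classification in Section 7.9.9*, which turns on whether the treatment SOP was followed. That section does not define the SOP, so whether 7.4.3 is part of it cannot be established.

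**Conclusion.** The point holds in a narrow form and should be fixed. Item 9 is wrong as written: it is a safety instruction inconsistent with, and weaker than, both device texts in the same document. The gap is limited to blanching during or directly after injection that has not yet been recognized as intravascular. Once recognition occurs, Appendix 1 applies; if blanching persists, item 9 already directs a call to the Medical Monitor.

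The 13-item comparison measures wording, not risk. The documents give no blanching rate, so no number of affected sessions or injuries can be stated. A reader might infer an unsafe design or a threat to the trial's conclusions. Neither follows: the defect is one item of wording, and it has no effect on efficacy inference, alpha or sample size.

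The conclusion assumes that 7.4.3 is a text the injector works from, and that silence on precedence means the IFUs do not automatically override it.

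**What to change.** Replace item 9 of Protocol 7.4.3, and only that item, with:

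> If blanching is seen during injection or directly after it, stop injecting immediately and massage the area gently until normal color returns. If normal color does not return, do not resume injection, contact the Medical Monitor, and treat as a suspected vascular occlusion using the skin infarction steps in Appendix 1.

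The last clause is needed because the Appendix 1 steps are headed for an identified infarction. A bare cross-reference would lead to steps whose stated condition is not yet met.

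Leave the PN40082 IFU unchanged. It already has the unconditional trigger, the pause and the directed massage, and its pause is compatible with this wording.

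The cost is a one-item amendment. Under Section 10.5, "Such revisions must be submitted to and have documented approval from the Sponsor and IRB prior to implementation". Some sessions will be interrupted briefly for blanching that would have cleared without action. No new visit, data item or supply is needed: Appendix 1 already lists hyaluronidase, aspirin and nitroglycerin paste as materials required on site.
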